7.7 PHYSICAL EXAMINATION

The complete physical examination will include routine examinations for the following:

- General Appearance
- Head, Ears, Eyes, Nose, Throat (HEENT)
- Lymph Nodes
- Heart/Cardiovascular abnormalities
- Respiratory
- Abdomen
- Genitourinary
- Musculoskeletal and Extremities
- Neurologic abnormalities Dermatologic abnormalities
- Any other body system for which an abnormality is noted and which, in the opinion of the Investigator, is relevant to the safety of the subject or could impact safety results for the subject; i.e., the abnormality is clinically significant (CS).

Each abnormality will be recorded and the Investigator will record an assessment of its clinical significance.

The complete physical examination will be conducted at the TE1, EOT2 and at Virologic Failure (VF) visit. Only symptom-directed physical examination will be performed during Screening Phase, at treatment and follow-up visits conducted within the clinic, and at unscheduled visits within the Treatment and Follow-up Phases.

7.8 ELECTROCARDIOGRAM

A 12-lead ECG will be conducted at EOT2 and results will be evaluated by the Investigator. The following parameters will be recorded: ventricular rate (beats per minute), PR interval (msec), QRS interval (msec), QT interval (msec), and QTc interval (msec). Additionally, the investigator will record the overall results of the ECG reading as either normal or abnormal, and as either not clinically significant or clinically significant. If abnormalities are observed, each will be recorded.

7.9 NEUROLOGICAL ASSESSMENT

Neurological assessment will be performed by the Principal Investigator (or delegated personnel) or a Neurologist during Screening Phase, at TE1, EOT2 and Virologic Failure (VF) visit.

The neurological assessment tool is based on the three question survey used by Simioni et al. [Simioni S, 2010]. Refer to [section 16.4](#) for further details. Additional assessment modalities can be used for further assessment as per Investigator's discretion.

7.10 VITAL SIGNS

Vital signs will be collected at all study visits performed at the clinic. Vital signs collected during the Treatment Extension Phase (*except for TE1*) will be performed post-treatment, assessed within 15 minutes following study treatment administration.

The following vital signs will be collected at all visits, unless otherwise stated:

- Seated blood pressure (taken after the subject has been seated for at least 5 minutes)
- Heart Rate
- Respiration Rate
- Temperature

7.11 CLINICAL LABORATORY ASSESSMENTS

Unless stated otherwise, blood and urine samples will be collected once every eight weeks according to the time points in the schedule of assessments for analysis of the following parameters:

7.11.1 Routine CBC

- Frequency of testing: At TE1, once every 12 weeks during Treatment Extension, EOT2 or Virologic Failure visit
- Includes hemoglobin, hematocrit (HCT), red blood cell (RBC) count, white blood cell (WBC) count, WBC differential count (%), absolute neutrophils count and platelets count.

7.11.2 Biochemistry

- Frequency of testing: At TE1, once every 12 weeks during Treatment Extension, EOT2 or Virologic Failure visit
- Biochemistry profile includes assessment of
 - Hepatic function indicators: total and direct bilirubin, alkaline phosphatase, aspartate aminotransferase (AST), alanine aminotransferase (ALT), total protein, LDH
 - Renal function indicators: BUN, creatinine
 - Electrolytes: sodium, potassium, chloride, calcium and bicarbonate

Other: glucose (random), cholesterol (total)

7.11.3 Coagulation indices

- Frequency of testing: At TE1, once every 12 weeks during Treatment Extension, EOT2 or Virologic Failure visit.
- Prothrombin time (PT) and International Normalized Ratio (INR)

7.11.4 Urinalysis

- Frequency of testing: At TE1, once every 12 weeks during Treatment Extension, EOT2 or Virologic Failure visit.
- Urine samples will be tested for color, appearance, specific gravity, pH, protein, glucose, occult blood, ketones, leukocyte esterase, nitrite, bilirubin, urobilinogen, and microscopic examination of urine sediment

7.11.5 Urine pregnancy test

- Frequency of testing: At first treatment visit (TE1) prior to treatment administration
- A urine sample will be collected from female subjects of childbearing potential. This test will be performed at the study site using a commercially available kit.

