1.6.1.4 Pregnancy

Risks to unborn babies are unknown at this time; pregnant females will be excluded from this study. Females of childbearing potential must have a negative pregnancy test prior to enrollment. Both male and female patients and their partners of childbearing potential must agree to use appropriate birth control methods throughout the study duration (excluding women who are not of childbearing potential and men who have been sterilized).

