3.3 ELIGIBILITY CRITERIA

3.3.1 Inclusion Criteria

[figure not shown]
Subjects must meet all of the following criteria to be included in the study:

1. Subjects who have completed 24 weeks of treatment in PRO 140_CD 02 or CD02_OpenLabel study, and Investigator believes subject requires continued access to PRO 140 in order to continue deriving clinical benefit and maintain HIV-1 viral suppression.
2. HIV-1 RNA <50 at T23 Visit in PRO140_CD02 or CD02_Open Label study
3. Both male and female patients and their partners of childbearing potential must agree to use 2 medically accepted methods of contraception (e.g., barrier contraceptives [male condom, female condom, or diaphragm with a spermicidal gel], hormonal contraceptives [implants, injectables, combination oral contraceptives, transdermal patches, or contraceptive rings], and intrauterine devices) during the course of the study (excluding women who are not of childbearing potential and men who have been sterilized). Females of childbearing potential must have a negative serum pregnancy test at Screening visit and negative urine pregnancy test prior to receiving the first dose of study drug.
4. Willing and able to participate in all aspects of the study, including use of SC medication, completion of subjective evaluations, attendance at scheduled clinic visits, and compliance with all protocol requirements as evidenced by providing written informed consent.

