- [6] Hemoglobin, Hematocrit (HCT), Red Blood Cells (RBC), White Blood Cells (WBC) with total and differential count, Absolute Neutrophil Count (ANC) and platelets.
- [7] Serum Biochemistry
 - Hepatic function indicators: total and direct bilirubin, alkaline phosphatase, aspartate aminotransferase (AST), alanine aminotransferase (ALT), total protein, Lactate dehydrogenase (LDH)
 - Renal function indicators: BUN, creatinine
 - Electrolytes: sodium, potassium, chloride, calcium and bicarbonate
 - Other: glucose (random), cholesterol (total)
- [8] Prothrombin time (PT) and International Normalized Ratio (INR)
- [9] Urine samples will be tested for color, appearance, specific gravity, pH, protein, glucose, occult blood, ketones, leukocyte esterase, nitrite, bilirubin, urobilinogen, and microscopic examination of urine sediment.
- [10] ONLY performed on women of childbearing potential. Subject will not be allowed to participate if the result is positive.
- [11] Plasma HIV-1 RNA and TruCount T Assay will be performed once every 4 weeks when subject comes to clinic. TruCount T Assay includes: CD3 %, CD4 %, CD8 %, Absolute Lymphocytes, CD3 cell count, CD4 cell count, and CD8 cell count
- [12] Injection Site Reaction will be assessed by the Investigator whenever IP administered at the clinic.
- [13] Monogram Biosciences Trofile® RNA and PhenoSense® Entry Assays [AMD3100 (CXCR4 inhibitor drug), Maraviroc and PRO 140 (CCR5 inhibitor drugs)]
- [14] Monogram Biosciences PhenoSense® GT Assay
- [15] Every 12 weeks during Treatment Extension.
- [16] Refer to [Section 7.11.10](#).

Table 4-2: Schedule of Assessments –Follow-Up (FU) Phase
(a) Subjects who do NOT experience virologic failure

Procedure/Assessments	Follow-Up Visit -1	Follow-Up Visit -2
	NVF-EFU1	NVF-EFU2
Window Period	2 weeks (±3 days) after EOT2 visit	4 weeks (±3 days) after EOT2 visit
Physical Examination	X ^[1]	X ^[1]
Vital Signs	X	X
Plasma HIV-1 RNA level	X	X
TruCount T assay	X	X
Adverse Events	X	X
Concomitant Medications	X	X

[1] Symptom-directed physical examination

(b) Subjects who experience virologic failure

Procedure/Assessments	Follow-Up Visit -1	Follow-Up Visit -2	Follow-Up Visit -3 ^[1]
	VF-EFU1	VF-EFU2	VF-EFU3
Window Period	4 weeks (±7 days) after VF visit	8 weeks (±7 days) after VF	12 weeks (±7 days) after VF
Physical Examination	X ^[2]	X ^[2]	X ^[2]
Vital Signs	X	X	X
Plasma HIV-1 RNA level	X	X	X
TruCount T assay	X	X	X
Adverse Events	X	X	X
Concomitant Medications	X	X	X

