5.2 SUBJECT WITHDRAWAL

A subject who enters the Treatment Extension Phase but does not complete the study, as defined in [Section 5.1](#), is considered to have prematurely withdrawn from the Study.

All subjects have the right to withdraw at any point during treatment without prejudice to future care. It will be documented whether or not each subject completed the clinical study. If for any subject, study treatment or observations were discontinued, the reason(s) will be recorded.

The Investigator can discontinue a subject at any time if it is considered medically necessary.

In addition, subjects WILL be withdrawn from the study, in consultation with the Medical Monitor and the Investigator, if any of the following are met:

- A subject is significantly non-compliant with the requirements of the protocol.
- The investigator determines that it is in the best interest of the subject.
- Subject chooses to withdraw or is withdrawn due to an adverse event
- A subject becomes pregnant

Note: *The pregnancy will be followed to term for safety follow-up. Relevant safety information collected after the study has completed will be reported as supplemental information.*

- Discontinuation of study by Sponsor

Premature withdrawal from the study MAY occur if, in consultation with the Medical Monitor and the Investigator, any of the following are met:

- A subject is treated with a prohibited medication.

- Major protocol violation

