7.11.6 Plasma HIV-1 RNA level and TruCount T Assay

- Frequency of testing: During Screening, at first treatment visit (TE1) prior to treatment administration, at least once every four weeks during Treatment Extension Phase, EOT2, at VF, and at all Virologic Failure Follow-up (VF-EFU) or Non- Virologic Failure Follow-up (NVF-EFU) visits.
- To assess antiretroviral therapeutic response to PRO 140

Note: *Plasma HIV-1 RNA level will be measured using Human Immunodeficiency Virus 1 (HIV-1), Quantitative, RNA (Taqman®) test.*

TruCount T Assay includes measurement of Absolute Lymphocytes, CD3 cell count, CD4 cell count, CD8 cell count, CD3%, CD4% and CD8%

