7.14 COVID-19 GUIDANCE

The purpose of this guidance is to inform sites how to proceed in light of the challenges faced by patients and clinical trial sites as a result of COVID-19 shelter-in-place mandates from state governments. The content of this letter is based on FDA Guidance on Conduct of Clinical Trials of Medical Products during COVID-19 Pandemic (18 Mar 2020).

- The current schedule of assessments requires subjects to visit the clinic at least once every four weeks for lab assessments. Subjects may still continue to receive treatment with PRO 140 if they are unable to visit the clinic.
- Site staff may visit subjects' homes to conduct study assessments and/or deliver PRO 140.
- Sites may ship PRO 140 to subjects' homes if subjects are unable to visit the clinic.
- If subjects are unable to visit the clinic at least once every four weeks lab assessments will be missed. If this occurs site staff should contact subjects weekly by phone to assess:
 - Compliance to study treatment
 - Potential adverse events
 - Changes in concomitant medications
- Sites should document phone calls and include confirmation of compliance to study treatment, and report any adverse events and/or changes in medications.
- Subjects who report positive tests results for COVID-19 should have the diagnosis recorded as an adverse event.
- Sites should clearly document reasons for failing to obtain required assessments (e.g., limitation imposed by COVID-19 leading to the inability to perform the protocol-specified assessment).
- Any changes in the study visit schedule or missed visit should be entered as protocol deviation in the EDC and reason should be documented as missed study visit or visit performed out of window period due to COVID-19.
- If subject is early withdrawn from the study due to COVID-19, the reason should be clearly documented in the End of Study (EOS) section in EDC as "study discontinuation due to COVID-19".

- Monitoring activities will be performed remotely until Centers for Disease Control (CDC) recommendations allow travel to resume.

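### No pregnancy test is scheduled after the first extension dose, although weekly dosing is open-ended, fetal risk is stated as unknown and pregnancy requires withdrawal

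*Protocol*

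**What the plan says.** The urine test has one scheduled time point (Protocol 7.11.5): "Frequency of testing: At first treatment visit (TE1) prior to treatment administration". Table 4-1 and the schedule in SAP Appendix 1 agree, each with a single mark in the TE1 pre-treatment column. Footnote 10 to Table 4-1 gives the test's purpose: "ONLY performed on women of childbearing potential. Subject will not be allowed to participate if the result is positive". It is an entry check.

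Inclusion criterion 3 in section 3.3.1 asks for a "negative serum pregnancy test at Screening visit and negative urine pregnancy test prior to receiving the first dose of study drug". Both tests come before the first extension dose. The serum test appears neither in the screening list in section 4.1 nor in Table 4-1.

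Three other provisions apply for as long as treatment lasts:

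- Section 1.6.1.4: "Risks to unborn babies are unknown at this time; pregnant females will be excluded from this study".
- Section 5.2 lists events that oblige withdrawal, in consultation with the Medical Monitor and the Investigator. One is "A subject becomes pregnant". Section 5.2.1 also lists pregnancy, as a reason for which stopping PRO 140 is recommended.
- Section 8.1: weekly dosing runs until virologic failure, withdrawal of consent, approval of PRO 140, or a sponsor decision to end development.

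**The concern.** The rules on pregnancy cover the whole treatment period, but the only scheduled checks on them come before it starts. A negative result at TE1 says nothing about a conception six months or two years later. Following the plan as written, a site could keep giving or shipping weekly PRO 140 through an unrecognised pregnancy without missing any required procedure.

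What is at stake is the safety of the woman and the fetus under a drug whose fetal risk the protocol calls unknown. Late recognition also leaves less time to plan a replacement regimen, and these subjects were enrolled because PRO 140 was judged necessary to a viable one.

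Reporting is not the gap. A pregnancy that becomes known must be reported and followed (Protocol 9.2), and its outcome is listed (SAP 7.2.9.3).

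**Working it through.** The plan gives no figure to reproduce. The check is a reading of every place where a later test could be scheduled, followed by a count.

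**Step 1. Where a test could appear**

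| Place | Pregnancy test listed? |
|---|---|
| Protocol 3.3.1, Screening | Serum, before first extension dose |
| Protocol 4.2.1, 7.11.5, Table 4-1 (TE1) | Urine, before first extension dose |
| Protocol 4.2.2 (later treatment visits, including EOT2 items) | No |
| Protocol 4.2.3 (VF visit) | No |
| Protocol 4.3.1, Table 4-2 (follow-up) | No |
| SAP Appendix 1 | TE1 pre-treatment only |

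Scheduled tests after the first extension dose: 0.

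**Step 2. What could detect a pregnancy on treatment instead**

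- Two-method contraception (3.3.1) and the exclusion of women planning pregnancy (3.3.2) make pregnancy less likely but do not detect it.
- Adverse-event questioning (9.1) and medication questioning at visits (7.6) depend on what the subject knows and mentions.
- Symptom-directed examination (4.2.2, 7.7) needs a symptom to direct it.
- Note a to Table 4-1 and section 4.4 allow the Investigator to add a test but do not require one.
- The urinalysis parameters in 7.11.4 do not include a pregnancy test.
- Under section 7.14, "Subjects may still continue to receive treatment with PRO 140 if they are unable to visit the clinic". The weekly phone call that replaces missed visits covers treatment compliance, adverse events and medication changes. Pregnancy is not on the list.

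**Step 3. What existing visits would allow**

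Urine is already collected on this timetable (7.11.4): "Frequency of testing: At TE1, once every 12 weeks during Treatment Extension, EOT2 or Virologic Failure visit". Viral load and T-cell counts are taken "at least once every four weeks during Treatment Extension Phase" (7.11.6). With one dose a week:

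- Doses between tests = test interval in weeks ÷ 1 week per dose. Every 12 weeks: 12 ÷ 1 = about 12. Every 4 weeks: 4 ÷ 1 = about 4. Current plan: no test after TE1, so the schedule sets no limit.
- Tests per year on treatment = 52 ÷ interval. Every 12 weeks: 52 ÷ 12 = 4.3, so 4. Every 4 weeks: 52 ÷ 4 = 13. Current plan: 0.

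The 12-week and 4-week intervals are taken from existing visits. The documents set no retest interval.

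**Step 4. How many women this might concern**

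The number of women of childbearing potential is not stated. As a rough guide only, protocol section 1.4.2 gives the sex mix of earlier studies of PRO 140 in HIV-positive subjects. Applied to 50 subjects:

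- CD01: 3/43 × 50 = 3.5
- 2101: 4/44 × 50 = 4.5
- CD01-Extension: 2/16 × 50 = 6.3
- 1302: 8/39 × 50 = 10.3

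That suggests roughly 3 to 10 women if the mix were similar, which is an assumption because those populations differ from the CD02 population. Not all would be of childbearing potential: median ages were 55.5 years in CD01 and 54.9 in CD01-Extension, though lower in 1302 (40.3) and 2101 (42.3).

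**The case against.** The strongest counter-case accepts that nothing is scheduled after TE1 and disputes the weight.

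- **The stop rule is softer than it looks.** Section 5.2.1, which governs stopping PRO 140 itself, only recommends it. That wording is there, but it does not cancel the mandatory withdrawal in 5.2, and both sections depend on someone knowing about the pregnancy.
- **An unlimited number of doses between tests is not the harm.** The harm is doses given during an unrecognised pregnancy. That is bounded by gestation and usually ends sooner, when symptoms or missed menses prompt a test. This is fair: the dose counts describe the schedule, not the risk to any one woman. It remains true that the schedule itself sets no bound.
- **Few women are likely to be affected, and all must use two contraceptive methods.** This stands and limits the size of the problem. It does not reduce the exposure of a woman who does become pregnant.
- **Tests at EOT2 and VF come late.** A test at EOT2 mainly documents exposure. A test at VF matters chiefly where PRO 140 continues while a new regimen is built. The periodic on-treatment test therefore does most of the work.
- **Urine at the VF visit is not certain.** The list in 4.2.3 omits urinalysis, while 7.11.4 and Table 4-1 include it. The weight of the text supports collection, but the lists should be aligned.

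**Conclusion.** The concern holds. The plan schedules no pregnancy test after the first extension dose, while dosing is weekly and open-ended, fetal risk is stated as unknown, and pregnancy requires withdrawal. Its own stop rule has no scheduled trigger.

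The size is modest. The number of women exposed to the gap cannot be computed from the documents and is probably small, and no planned analysis changes. The count of 0 tests rests on the text alone. The comparisons with 12-weekly and 4-weekly testing assume that the existing visits are used and kept. The change should be made because it closes a real safety gap at very little cost.

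**What to change.** In Table 4-1, sections 7.11.5, 4.2.2 and 4.2.3, and SAP Appendix 1, add the on-site urine pregnancy test for women of childbearing potential, at least at the 12-weekly urinalysis visits and at EOT2 and VF. Using the 4-weekly clinic visits instead would shorten the gap further. Add urinalysis to the 4.2.3 list so that it matches 7.11.4. In section 7.14, add a pregnancy question to the weekly call for subjects who miss clinic visits. SAP 7.2.9.2 already lists all urine pregnancy results, so the new ones need no change of method.

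The cost is a few kits and minutes per eligible woman, using the kind of kit already used at TE1. Urine is already collected at the 12-weekly, EOT2 and VF visits; 4-weekly testing would need extra samples. The change also needs a minor protocol amendment with IRB approval, possibly a consent-form update (11.3), and a matching edit to the SAP schedule.

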7.11.6 Plasma HIV-1 RNA level and TruCount T Assay

- Frequency of testing: During Screening, at first treatment visit (TE1) prior to treatment administration, at least once every four weeks during Treatment Extension Phase, EOT2, at VF, and at all Virologic Failure Follow-up (VF-EFU) or Non- Virologic Failure Follow-up (NVF-EFU) visits.
- To assess antiretroviral therapeutic response to PRO 140

Note: *Plasma HIV-1 RNA level will be measured using Human Immunodeficiency Virus 1 (HIV-1), Quantitative, RNA (Taqman®) test.*

TruCount T Assay includes measurement of Absolute Lymphocytes, CD3 cell count, CD4 cell count, CD8 cell count, CD3%, CD4% and CD8%

7.11.7 HIV-1 Trofile® Assay

- Includes:
 - a. Trofile® RNA AssayTrofile® RNA is the primary assay used to assess HIV-1 co-receptor tropism status.
- Frequency of testing: At Virologic Failure visit

7.11.8 HIV-1 Drug Resistance Assay

- Includes:

- a. PhenoSense® GT

PhenoSense® GT is a combination resistance test for three classes of antiretroviral drugs (i.e., nucleoside/nucleotide, non-nucleoside, and protease inhibitors), that provides both phenotypic and genotypic results from the same blood sample (viral load \geq 500 copies/ml).

- Frequency of sample collection: At Virologic Failure visit

7.11.9 HIV-1 PhenoSense® Entry assay

- Frequency of testing: At Virologic Failure visit, in conjunction with HIV-1 tropism testing
- With AMD3100 (CXCR4 inhibitor drug), Maraviroc and PRO 140 (CCR5 inhibitor drugs).

7.11.10 CCR5 Receptor Occupancy

- To assess the number CCR5 receptors on patients' CD4 cell surface. Of those CCR5 receptors, the test will also assess the number and percentage of CCR5 receptors that are covered by PRO 140.
- Frequency of testing: This assessment will be performed up to 5 times at different treatment visits. Blood will be taken prior to PRO 140 injection (trough sample) and 24-48 hours (peak sample) after the PRO 140 injection to check for CCR5 occupancy, and correlative analysis will be performed with PRO 140 PK concentration and HIV-1 RNA levels.

All laboratory reports will be reviewed by the Investigator.

Post-treatment abnormal results that are considered by the Investigator to be clinically significant will be recorded as adverse events. If the Investigator judges it necessary, testing may be repeated in order to make the determination of clinical significance. Validated, quality-controlled laboratory data will be transferred to the main database for analyses.

7.12 INVESTIGATIONAL PRODUCT ADMINISTRATION

Refer to [Section 6.4](#) for details.

